1. INTRODUCTION

This is a multicenter, randomized, double-blind, vehicle-controlled study with an open-label treatment extension period in adult participants (age ≥ 18 years) with nonsegmental vitiligo who have depigmented areas including $\geq 0.5\%$ BSA on the face, ≥ 0.5 F-VASI, $\geq 3\%$ BSA on nonfacial areas, and ≥ 3 T-VASI. Total body involved vitiligo area (facial and nonfacial) should not exceed 50% BSA. Approximately 60 participants will be randomized 2:1 to receive initial double-blind study treatment (ruxolitinib 1.5% cream:vehicle cream) administered BID for 24 weeks. Participants will be stratified by age (≤ 40 years old and > 40 years old).

During the study, participants will apply study drug to depigmented areas on the face and body up to 20% T-BSA (facial and nonfacial). After completion of the Week 24 assessments from the double-blind treatment period, eligible participants will be offered the opportunity to continue the study in the 28-week, open-label, treatment extension period. Participants initially randomized to vehicle cream will be crossed over to active drug (ruxolitinib 1.5% cream BID), and participants initially randomized to ruxolitinib cream will continue to receive treatment with ruxolitinib 1.5% cream BID. Following the last application of ruxolitinib cream at Week 52, there will be a 30-day safety follow-up period.

Section 2 of the Protocol provides a detailed description of the investigational product, target patient population, rationale for doses to be examined, and potential risks and benefits of treatment with ruxolitinib cream.

The purpose of this SAP is to provide details of the statistical analyses that have been outlined in the INCB 18424-214 Protocol. The scope of this plan will be executed by the Department of Biostatistics or designee. The details of the analysis methodology of biomarkers and pharmacodynamics and results will appear in a separate report.

2. STUDY INFORMATION, OBJECTIVES, AND ENDPOINTS

2.1. Protocol and Case Report Form Version

This SAP is based on INCB 18424-214 Protocol dated 03 MAR 2021 and CRFs approved 09 APR 2021. Unless superseded by an amendment, this SAP will be effective for all subsequent Protocol amendments and CRF versions.

2.2. Study Objectives and Endpoints

Table 1 presents the objectives and endpoints.

Table 1:Objectives and Endpoints

Objectives	Endpoints
Primary	
To evaluate the change in immune biomarkers in participants with vitiligo.	Percentage change from baseline in immune biomarkers, including CXCL10, at Week 4, Week 12, and Week 24.
Secondary	
To correlate the change in key serum and skin biomarkers of vitiligo to efficacy.	Correlation of key skin inflammatory biomarkers of vitiligo in target lesions to efficacy readouts at Week 12 and Week 24.
To assess the safety and local tolerability of ruxolitinib cream.	The frequency and severity of AEs.

3. STUDY DESIGN

This is a multicenter, randomized, double-blind, vehicle-controlled study with an open-label treatment extension period in adult participants (age ≥ 18 years) with nonsegmental vitiligo who have depigmented areas including $\geq 0.5\%$ BSA on the face, ≥ 0.5 F-VASI, $\geq 3\%$ BSA on nonfacial areas, and ≥ 3 T-VASI. Total body involved vitiligo area (facial and nonfacial) should not exceed 50% BSA. Approximately 60 participants will be randomized 2:1 to receive initial double-blind study treatment (ruxolitinib 1.5% cream:vehicle cream) administered BID for 24 weeks. Participants will be stratified by age (≤ 40 years old and > 40 years old).

After completion of the Week 24 assessments from the double-blind treatment period, eligible participants will be offered the opportunity to continue the study in the 28-week, open-label, treatment extension period. Participants initially randomized to vehicle cream will be crossed over to active drug (ruxolitinib 1.5% cream BID), and participants initially randomized to ruxolitinib cream will continue to receive treatment with ruxolitinib 1.5% cream BID.

The study schema is shown below in Figure 1. All participants will have follow-up assessments 30 (+7) days after the last application of study drug.

Double-Blind **Treatment Extension** Screening (up to 42 days) (24 weeks) Randomization (2:1) (28 weeks) **Rux Cream** • Adult aged ≥ 18 years Follow-Up 1.5% BID (n =40) Non-segmental vitiligo (30 days) Rux Cream \geq 0.5% BSA on the face and \geq 0.5 F-VASI \geq 3% BSA on nonfacial areas and \geq 3 T-VASI 1.5% BID Total not to exceed 50% BSA Vehicle BID (n =20) N= 60 12 24 28 40 EOS Week 0 4 52 (Day 1) FOT

Figure 1: Study Design Schema

3.1. Randomization

Approximately 60 participants will be randomized 2:1 to receive initial double-blind study treatment (ruxolitinib 1.5% cream BID:vehicle cream BID) for 24 weeks. Participants will be stratified by age (≤ 40 years old and > 40 years old).

3.2. Control of Type I Error

No alpha control will be implemented. Unless otherwise specified, all CIs provided will be at the 95% confidence level.

3.3. Sample Size Considerations

Due to the exploratory nature of the study, the sample size is not based on calculation of statistical power. The sample size is considered to be sufficient to obtain adequate safety, tolerability, tolerability,

Approximately 60 participants will be randomized 2:1 to ruxolitinib 1.5% cream BID or vehicle cream BID to ensure approximately 45 participants will have multiple biomarker data (eg, CXCL10; Rashighi and Harris 2015) available at Week 24.

On the basis of the results of a Phase 2 study (INCB 18424-211), the anticipated difference in percentage change from baseline in CXCL10 between ruxolitinib 1.5% cream BID and vehicle cream BID is 22% (STD = 0.25%). Using a 2-sample t-test, the sample size of 45 will provide great power ($\geq 80\%$) to detect such difference with a 2-sided alpha of 0.10.

3.4. Schedule of Assessments

Refer to Protocol dated 03 MAR 2021 for a full description of all study procedures and assessment schedules for this study.

4. DATA HANDLING DEFINITIONS AND CONVENTIONS

4.1. Scheduled Study Evaluations and Study Periods

4.1.1. Day 1

Day 1 is the date that the first application of ruxolitinib cream or vehicle cream is administered to the participants in the specific period.

For randomized participants not treated with any study drug, Day 1 is defined as the date of randomization.

4.1.2. Study Day

If a visit/reporting date is on or after Day 1, then the study day at the visit/reporting date will be calculated as

Day # = (visit/reporting date - Day 1 date + 1).

If the visit/reporting date is before Day 1, then the study day at the visit/reporting date will be calculated as

Day # = (visit/reporting date - Day 1 date).

A study day of -1 indicates 1 day before Day 1.

4.1.3. Baseline Value

Baseline is the last nonmissing measurement obtained before the first application of ruxolitinib cream or vehicle cream in the double-blind period.

For randomized participants not treated with any study drug, baseline is defined as the last nonmissing assessment before randomization for all parameters.

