9.2. Adverse Events

9.2.1. Adverse Event Definitions

A TEAE is any AE either reported for the first time or worsening of a pre-existing event after the first application of study drug and within 30 days of the last application of study drug. For participants who cross over treatments, the first application date is period-specific, and the end date is 30 days after the last application date in the period, or the day before the first application date in the next period, whichever comes first. Analysis of AEs (as discussed below) will be limited to TEAEs, but data listings will include all AEs regardless of their timing in relation to study drug application.

Adverse events will be tabulated by MedDRA PT and SOC. Severity of AEs will be graded using the NCI CTCAE v5.0. The CTCAE reporting guidelines and grading details are available on the Cancer Therapy Evaluation Program website.

The subset of AEs considered by the investigator to be related to study drug will be considered to be treatment-related AEs. If the investigator does not specify the relationship of the AE to study drug, the AE will be considered to be treatment-related. The incidence of AEs and treatment-related AEs will be tabulated. Serious AEs will also be tabulated.

Any missing onset date, causality, or severity must be queried for resolution. Unresolved missing causality and severity will be handled according to the following rules:

- An unresolved missing causality will be considered treatment-related.
- An unresolved missing severity will be identified as an unknown severity.

For purposes of analysis, all AEs will be considered TEAEs unless the AE can unequivocally be defined as not treatment-emergent.

Application site reactions are AEs that occur at the site of study drug application. A summary of ASRs will be provided. Exposure-adjusted summaries will be provided for the safety population including cumulative TEAEs.

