9.3. Clinical Laboratory Tests

9.3.1. Laboratory Value Definitions

All laboratory assessments will be performed using a central laboratory except for urine pregnancy tests (as applicable). Laboratory values and change from baseline values will be summarized descriptively by visit, and non-numeric test values will be tabulated when necessary.

The baseline value will be determined using the last nonmissing value collected before the first application, prioritizing scheduled assessments for baseline identification over unscheduled visits. The last record before application in the highest priority will be considered the baseline record. For baseline laboratory candidates with the same date and time in the same priority category, additional rules may be provided after consultation with the medical monitor to delineate which value will be defined as baseline.

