9.3.2. Laboratory Value Summaries

Actual values and changes from baseline in clinical laboratory test results will be summarized using descriptive statistics. Laboratory test values outside the normal range will be assessed for severity based on the normal ranges for the clinical reference laboratory. The incidence of abnormal laboratory values will be tabulated.

Laboratory data will be classified into Grades 1 through 5 using CTCAE v5.0. The following summaries will be produced for the laboratory data:

- Number and percentage of participants with worst postbaseline CTCAE grade (regardless of baseline value). Each participant will be counted only for the worst grade observed postbaseline.
- Shift tables from baseline to the worst postbaseline value using CTCAE grade.
- For laboratory parameters where CTCAE grades are not defined, shift tables to the worst postbaseline value using the low/normal/high classifications based on laboratory reference ranges.

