10. VITAL SIGNS

Values at each scheduled visit, change, and percentage change from baseline for vital signs, including systolic blood pressure, diastolic blood pressure, pulse, temperature, and respiratory rate, will be summarized descriptively.

Normal ranges for vital sign values are defined in Table 2. For participants exhibiting vital sign abnormalities, the abnormal values will be listed along with their assigned treatment group. Alert vital signs are defined as an absolute value outside the defined normal range and percentage change > 25%. The abnormal values for participants exhibiting alert vital sign abnormalities will be listed.

Parameter	Low Threshold	High Threshold	
Systolic blood pressure	\geq 85 mmHg	≤ 155 mmHg	
Diastolic blood pressure	\geq 40 mmHg	$\leq 100 \text{ mmHg}$	
Pulse	\geq 45 bpm	$\leq 100 \text{ bpm}$	
Temperature	≥ 35.5°C	≤ 38°C	
Respiratory rate	\geq 8 breaths/min	\leq 24 breaths/min	

Table 2:Normal Ranges for Vital Sign Values

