3.2.11.1.X	Summary of Treatment-Emergent Adverse Events Leading to Discontinuation of Study Drug by MedDRA System Organ Class and Preferred Term	Safety/TEE
Laboratory values and vital signs		
3.3.1.X	Summary of Laboratory Values – Hematology	Safety/TEE
3.3.3.X	Shift Summary of Hematology Laboratory Values in CTCAE Grade – To the Worst Abnormal Value	Safety/TEE
3.3.4.X	Summary of Laboratory Values – Chemistry	Safety/TEE
3.3.6.X	Shift Summary of Chemistry Laboratory Values in CTCAE Grade – To the Worst Abnormal Value	Safety/TEE
3.4.1.X	Summary of Systolic Blood Pressure	Safety/TEE
3.4.2.X	Summary of Diastolic Blood Pressure	Safety/TEE
3.4.3.X	Summary of Pulse	Safety/TEE
3.4.4.X	Summary of Respiration Rate	Safety/TEE
3.4.5.X	Summary of Body Temperature	Safety/TEE

Note: For AE tables ending with X, separate tables will be provided for the double-blind period (safety population) and treatment extension period (TEE population).

Note: For AE tables ending with Y, tables will be provided for the overall treatment period (double-blind and treatment extension periods). Participants who cross over should be included in both treatment groups.

Note: For laboratory values/vital sign tables ending with X, separate tables will be provided for the double-blind period (safety population) and treatment extension period (TEE population).

Listings

Listing No.	Title		
Demographic and baseline characteristics			
2.1.1	Participant Enrollment and Disposition Status		
2.1.2	Participants Who Discontinued Treatment or Discontinued From Study Due to COVID-19		
2.1.3	Participants With Assessments Not Done Due to COVID-19 Pandemic		
2.2.1	Protocol Deviations		
2.2.2	Participant Inclusion and Exclusion Criteria Violations		
2.3	Analysis Populations		
2.4.1	Demographic Characteristics		
2.4.2	Baseline Disease Characteristics		
2.4.3	Medical History		
2.4.4	Prior and Concomitant Medications		
2.4.5	Prior Medications for Vitiligo		
2.5.1	Study Drug Exposure and Compliance		
-			
-			
Adverse even	ts		
2.7.1	Adverse Events		
2.7.2	Adverse Events Leading to Study Drug Discontinuation		
2.7.3	Serious Adverse Events		
2.7.4	Treatment-Related Adverse Events		
2.7.5	Adverse Events With a Fatal Outcome		
2.7.6	Adverse Events Leading to Interruption of Study Drug		
2.7.8	Grade 3 or Higher Adverse Events		
2.7.9	Application Site Reactions		
Laboratory d	lata		
2.8.1.1	Clinical Laboratory Values – Hematology		
2.8.1.2	Clinical Laboratory Values – Chemistry		

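### In the extension laboratory and vital-sign tables, the single double-blind baseline mixes change on vehicle with change on ruxolitinib for participants who cross over

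*SAP*

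**What the plan says.** SAP 4.1.3 defines baseline once, for all parameters: "Baseline is the last nonmissing measurement obtained before the first application of ruxolitinib cream or vehicle cream in the double-blind period". Protocol 10.4.3 also ties baseline to the first application of either cream and does not reset it later. The laboratory rule in SAP 9.3.1 reads "The baseline value will be determined using the last nonmissing value collected before the first application" and names no period. SAP 10 plans "Values at each scheduled visit, change, and percentage change from baseline for vital signs" and gives vital signs no baseline of their own.

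Several extension outputs depend on that baseline. SAP 9.3.2 plans "Shift tables from baseline to the worst postbaseline value using CTCAE grade". A note in SAP Appendix A adds: "For laboratory values/vital sign tables ending with X, separate tables will be provided for the double-blind period (safety population) and treatment extension period", the latter in the treatment-extension evaluable (TEE) population. SAP 5.2 shows crossovers as their own extension group, separate from those who received ruxolitinib throughout.

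Two neighbouring definitions are tied to the period. SAP 4.1.1 dates Day 1 from the first application in the period concerned. SAP 9.2.1 says, for adverse events: "For participants who cross over treatments, the first application date is period-specific".

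**The concern.** The extension tables are meant to describe safety while everyone is on ruxolitinib. For crossovers, however, the reference value predates about 24 weeks of vehicle. A grade shift that arose on vehicle and is still present after Week 24 appears as an extension-period shift. A rise on vehicle followed by an equal fall on ruxolitinib appears as no change. The table alone cannot tell a reader which happened.

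The same people in the same period are thus measured from two starting points: adverse events from the first ruxolitinib application, laboratory and vital-sign change from the start of the double-blind period. No reason is given for the difference. Protocol 2.2.1 gives further evaluation of the safety of ruxolitinib cream as one purpose of the open-label period, so these tables serve a stated aim.

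**Working it through.** No stated sample size, power or alpha depends on this definition, so there is no plan figure to reproduce. The check traces the definition and then sizes the effect under assumptions.

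**1. Does anything override SAP 4.1.3?** Nothing visible does. SAP 9.3.1 omits the period, SAP 10 is silent, and Appendix A asks for extension tables without naming a baseline for them.

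**2. What does the extension change contain?** For a crossover participant:

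- extension value − pre-vehicle value = (Week 24 value − pre-vehicle value) + (extension value − Week 24 value)

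The first bracket arose wholly on vehicle if the Week 24 value was taken before the first ruxolitinib application. Both brackets enter the tabulated change. The laboratory shift table uses the same reference. So does the alert rule ("Alert vital signs are defined as an absolute value outside the defined normal range and percentage change > 25") if its percentage change is measured from baseline, which SAP 10 does not spell out.

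**3. Which outputs do not use the baseline value?** Actual values by visit, listings of values, and "Number and percentage of participants with worst postbaseline CTCAE grade (regardless of baseline value"), also in SAP 9.3.2.

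**4. Is a pre-ruxolitinib value available?** Protocol Table 3 schedules haematology, chemistry and vital signs at Week 24. Protocol 8.1.4 places safety blood draws before the in-clinic application. No passage orders vital signs relative to that application.

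**5. Which extension values are postbaseline?** The SAP does not say. A footnote to Protocol Table 3 counts Week 24 as the first open-label visit, so a Week 24 value obtained wholly on vehicle could itself be tabulated as an extension result.

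**6. How large is the effect?** SAP Figure 1 puts 20 participants on vehicle, the upper limit for the crossover column. One participant is 1/20 = 5.0 percentage points, and more if fewer cross over (for example 1/15 = 6.7).

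The documents give no shift rates. Assume independent participants, no ruxolitinib effect, a probability *p* that a shift arises on vehicle, and a probability *q* that it persists into the extension.

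- Expected carried-over shifts = 20 × p × q
- Chance of at least one = 1 − (1 − pq)^20

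| p (assumed) | q (assumed) | Expected shifts | Chance of at least one |
|---|---|---|---|
| 5% | 25% | 20 × 0.05 × 0.25 = 0.25 | 1 − 0.9875^20 = 22% |
| 10% | 50% | 20 × 0.10 × 0.50 = 1.0 | 1 − 0.95^20 = 64% |
| 20% | 100% | 20 × 0.20 × 1.00 = 4.0 | 1 − 0.80^20 = 99% |

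With a baseline taken just before the first ruxolitinib application, these persisting shifts would not count as new, so the expected number in this simple model is 0.

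**The case against.** A fixed study baseline is a legitimate convention. An adverse-event onset window and a change-from-baseline reference answer different questions and need not match. The other planned outputs also allow partial separation. Vehicle-period shifts appear in the double-blind tables, values are summarised by visit, and participant-level listings are practical to read for about 20 people. With a single baseline, mean change after Week 24 can be approximated by subtracting the Week 24 mean change from the later one, apart from dropouts. SAP 9.3.1 could be read as period-specific, and the sample displays, which are in a separate document, might settle the handling.

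Much of this stands, and it limits the point to the shift tables and the change columns. It does not remove it. A shift table cannot be decomposed by subtraction, a fixed baseline for crossovers is not justified anywhere in the SAP, and reading 9.3.1 as period-specific would put it in conflict with 4.1.3.

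Two stronger readings are tempting and are not supported:

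- **That vehicle shifts are reported as ruxolitinib shifts outright.** Crossovers have their own labelled column and are not pooled with continuing ruxolitinib participants in these tables. The label shows that they crossed over, but not when a shift arose.
- **That this obscures an established haematological risk of the cream.** Protocol 2.3 ties anaemia, thrombocytopenia and neutropenia to oral ruxolitinib and expects no clinically significant haematology change from topical use. It describes the Phase 2 red-cell and platelet changes as minor and mostly within normal limits.

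Extension entry also requires the absence of safety issues (Protocol 4.1), and Protocol 6.5.1 provides for interruption or discontinuation after more severe laboratory abnormalities. Carried-over shifts would therefore be mainly low grade.

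**Conclusion.** The point holds within narrow limits. As written, SAP 4.1.3 makes the extension laboratory shifts, and the laboratory and vital-sign changes from baseline, a mixture of vehicle and ruxolitinib change in the crossover column. That is out of step with the SAP's own period-specific Day 1 and adverse-event window.

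The consequence is descriptive and involves at most about 20 participants. The randomised double-blind comparison, the biomarker endpoint and the adverse-event summaries are unaffected.

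The range of 0.25 to 4 carried-over shifts rests wholly on assumed rates of onset and persistence. A reader might take the upper end as a forecast, but the documents contain nothing that would support one. What is firm is that each such shift would be at least 5 percentage points of the column. The change is worth making because it is cheap and the values it needs are already scheduled.

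**What to change.** Amend SAP 4.1.3, 9.3.1 and 10 as follows:

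1. For extension-period laboratory and vital-sign tables, baseline for vehicle-to-ruxolitinib participants is the last nonmissing value before the first open-label ruxolitinib application. Week 24 vital signs qualify only if they were recorded before that application.
2. Extension postbaseline values are those obtained after the first open-label application, so that a Week 24 value taken on vehicle cannot enter as an extension result.
3. The continuing ruxolitinib group keeps the double-blind baseline, and a footnote states the two definitions.

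Because Protocol 10.4.3 also gives a single baseline, record the change in SAP 12.1.

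The cost is a few sentences, a second baseline flag in the analysis data and a footnote. No new data are needed and the double-blind analysis does not change. The real drawback is that one table would then hold two baselines: at Week 52, change spans about 52 weeks in the continuing group and about 28 weeks (52 − 24) in the crossover group, so the two columns should not be compared directly.

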4.1.4. Handling of Missing and Incomplete Data

In general, values for missing data will not be imputed unless methods for handling missing data are specified in this section or relevant sections.

4.1.5. Handling of Missing and Incomplete Dates

In general, values for missing dates will not be handled unless methods for handling missing dates are specified in this section or relevant sections. The original reported dates collected on the eCRF should be used in all relevant listings. The following rules will be used for handling partial dates for analyses requiring dates.

When calculating the time since diagnosis of vitiligo, a partial vitiligo diagnosis date will be handled as follows in the calculation:

- If only the day is missing, then the first day of the month will be used.
- If both the month and day are missing, then 01 JAN of the year will be used.
- If the diagnosis date is completely missing, then the time since diagnosis will not be calculated.

When the date of the last application is used in deriving variables such as duration of treatment or TEAE flag, a missing or partial date of the last application will be handled as follows:

- If only the day is missing, then the earlier date of the last day of the month or the date that the participant discontinued treatment will be used.
- If both the month and day are missing, then the earlier date of 31 DEC of the year or the date that the participant discontinued treatment will be used.
- Otherwise, the earlier date of treatment discontinuation date, end of study date, last contact date, or the cutoff date will be used as the date of the last application.

